#### **Secondary Outcome: Overall and Progression free survival / Safety**

*Survival:* Assuming full enrollment of 30 patients, both cohorts will be combined for assessment of secondary outcome of one-year overall survival. Kaplan-Meier (1958) curves will be generated for overall (OS) and progression free survival (PFS); the latter endpoint will be defined as the time from enrollment until disease progression or death from any cause. Median OS and PFS will be estimated along with 90% confidence intervals using the method of Brookmeyer and Crowley (1982). Duration of response will be determined as the time from response until disease progression or death among the subset of patients who respond, and estimated by Kaplan-Meier. The disease control rate (CR+PR+SD) and 90% confidence interval will also be determined.

*Toxicity:* Toxicities will be summarized in tabular form by type and severity and incidence rates generated.

Protocol #: UC IRB17-1539  
Version Date: 1/23/2018

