### 3.2 Secondary Objective(s) & Hypothesis

(1) **Objective:** 1-year Progression-free (PFS) and Overall (OS) survival

**Hypothesis:** Combined PD-1 blockade with pembrolizumab + epacadostat in HNSCC patients will lead to improved 1-year survival in patients who a) progress on prior anti-PD-1/PD-L1 therapy on, and/or b) compared to patients who progress on 2nd line chemotherapy.

(2) **Safety**

Protocol #: UC IRB17-1539

Version Date: 04/24/2019

**Hypothesis:** Combined treatment with pembrolizumab and epacadostat will be safe and tolerable in HNSCC patients.

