## **5.0 METHODOLOGY**

### **5.1 Entry Criteria / Eligibility**

#### **5.1.1 Diagnosis/Condition for Entry into the Trial**

#### **5.1.2 Subject Inclusion Criteria**

In order to be eligible for participation in this trial, the subject must fulfill the following entry criteria:

1. Patients must have histologically confirmed squamous cell carcinoma of the head and neck (unresectable and not amenable to curative intent therapy)
2. Meet criteria for either the Acquired Resistance OR the Suboptimal Benefit Cohort
  - a. **Acquired Resistance is defined as (i and ii must both be met):**
    - i. **Prior *benefit* from anti-PD-1/PD-L1 therapy defined as a) prior response, *and/or* b)  $\geq 5$  months of stable disease (SD). Intervening therapies are allowed.**
    - ii. **Progressive Disease (PD) on recent scans**
  - b. **Suboptimal Benefit is defined as (i and ii must both be met):**
    - i. **Prolonged stable disease  $\geq 5$  months OR Suboptimal response ( $>10\%$  &  $<50\%$  shrinkage per RECIST at any evaluation timepoint)**
    - ii. **Ongoing stable disease on recent scans**
    - iii. **Last treatment with an anti-PD-1/PD-L1 agent within 6 weeks prior to starting protocol treatment**
3. Archival tissue for PD-L1 staining (alternatively a new biopsy (core) at baseline can be used). A minimum of 10 slides is required (unless approval from the PI is obtained)
4. Measurable disease per RECIST 1.1.
5. Known HPV status
6. ECOG performance status 0 or 1
7. Be willing and able to provide written informed consent/assent for the trial.
8. Be  $\geq 18$  years of age on day of signing informed consent.
9. Demonstrate reasonable organ function as defined in
10. Table 1, all screening labs should be performed within 10 days of treatment initiation.

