### **5.10 Subject Replacement Strategy**

Patients who receive 0, or only 1 dose only will be replaced due to inadequate treatment exposure. An intention to treat analysis will be performed as a secondary analysis, but for the primary analysis only patients with adequate treatment exposure to 2 or more doses of pembrolizumab will be included.

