## 8.0 STATISTICAL ANALYSIS PLAN

### 8.1 Statistical Analysis Plan

**This study includes two cohorts. These will be handled as parallel cohorts/trials with the same statistical assumptions for both cohorts:**

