#### **Primary Outcome: Response rate**

Clinical and pathologic response rates will be determined and 90% confidence intervals obtained using the exact binomial distribution.

A Simon's two-stage design (Simon, 1989) will be used – using the Minimax variant - for both cohorts. The null hypothesis that the true response rate is 3% [ $p_0$ ] (*assuming poor efficacy of e.g. pembrolizumab treatment in patients, who have failed prior PD-1/PD-L1 therapy*) will be tested against a one-sided alternative. In the first stage, 10 [ $n_1$ ] patients will be accrued. If there are no responses [ $r_1$ ] in these 10 [ $n_1$ ] patients, the study will be stopped.

Otherwise, 5 additional patients will be accrued for a total of 15 [ $n$ ] patients. The null hypothesis will be rejected if 2 or more responses are observed in 15 patients. This design yields a type I error rate of 0.0667 and 80% power when the true response rate is 20%.

A response rate of 20% would be considered clinically meaningful for HNC in the absence of alternative treatment options in the 2nd/3rd line setting (after PD-1/PD-L1 failure) and further development of pembrolizumab + epacadostat would proceed.

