## 8.2 Sample Size

Sample size for each cohort is up to 15 patients (total of up to 30 patients).

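### Section 8.1 pools one-year overall survival across two cohorts that enter with different disease status; it should also be reported by cohort

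*Combined protocol and SAP*

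**What the plan says.** The secondary-outcome part of 8.1 gives one rule for one-year survival: "Assuming full enrollment of 30 patients, both cohorts will be combined for assessment of secondary outcome of one-year overall survival". It then plans Kaplan-Meier curves for OS and PFS, medians with 90% confidence intervals, and the disease control rate (CR+PR+SD). It does not say whether these are pooled or by cohort.

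Four other places bear on this:

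- The opening of 8.1 says of the two cohorts: "These will be handled as parallel cohorts/trials with the same statistical assumptions for both cohorts".
- Section 5.1.2 requires "Progressive Disease (PD) on recent scans" for the Acquired Resistance cohort and "Ongoing stable disease on recent scans" for the Suboptimal Benefit cohort.
- Section 3.2 names the secondary objective as "1-year Progression-free (PFS) and Overall (OS) survival". Its hypothesis is incompletely worded, but its first limb is about improved one-year survival in patients whose disease progresses on earlier PD-1/PD-L1 treatment.
- Section 8.2 sets 15 per cohort and 30 in total as upper limits. Under the two-stage rule, accrual ends after the first 10 patients if none responds.

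**The concern.** The pooling rule departs from the parallel handling that 8.1 announces, and it does so for an endpoint on which the two entry states could plausibly matter. Progression and ongoing disease control are different starting points for a survival clock.

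At full enrolment half the pool entered with stable disease, so the pooled figure describes neither cohort. It cannot speak to the first limb of the 3.2 hypothesis, for which the Acquired Resistance cohort is the closer match. Nor can it separate a uniform result from a split one: 12/30 (40%) arises from 6/15 and 6/15, or from 3/15 and 9/15.

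The disease control rate raises a related question of interpretation. In the Suboptimal Benefit cohort stable disease is an entry condition, so a patient who does not change counts as controlled. In the Acquired Resistance cohort stable disease means that progression has been halted.

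What is at stake is how clearly a descriptive secondary endpoint can be read.

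**Working it through.** **1. The plan's own design figures (8.1).** Each cohort stops with 0 responses in 10; otherwise 5 more are accrued, and the null is rejected with 2 or more responses in 15.

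P(reject) = 1 − P(0 of 10) − P(1 of 10) × P(0 of 5)

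- At 3%: 1 − 0.7374 − 0.2281 × 0.8587 = 0.0667, as stated.
- At 20%: 1 − 0.10737 − 0.26844 × 0.32768 = 0.8047, consistent with the stated 80%.

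**2. How often the cohort mix differs from 15:15.** P(0 of 10) is 0.97^10 = 0.7374 at a 3% response rate and 0.80^10 = 0.1074 at 20%. Reaching 30 needs both cohorts to pass stage 1. Taking the cohorts as independent, P(30 not reached) is:

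- both 20%: 1 − 0.8926² = 0.203
- one 3%, one 20%: 1 − 0.2626 × 0.8926 = 0.766
- both 3%: 1 − 0.2626² = 0.931

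The stopping sentence ends "patients, the study will be stopped". If that means the whole study rather than one cohort, these three probabilities do not change, because 30 still needs both cohorts to pass. They count design places and assume that accrual pauses at 10, a pause that 8.1 does not state. Section 5.10 also replaces some patients: "Patients who receive 0, or only 1 dose only will be replaced due to inadequate treatment exposure". Enrolled totals are therefore not fixed at 20, 25 or 30.

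**3. Share of the pool that entered with stable disease.** Acquired Resistance : Suboptimal Benefit

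- 15:15 gives 15/30 = 50%
- 15:10 gives 10/25 = 40%
- 10:15 gives 15/25 = 60%

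**4. What pooling does to the figure.** Pooled OS = (n1·p1 + n2·p2)/(n1 + n2). The documents give no one-year OS by cohort; section 4.2.4.1 has one benchmark, about 30% alive at one year. Assume p1 = 30% (Acquired Resistance) and p2 = 30% to 70% (Suboptimal Benefit), with no drug effect.

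- At 15:15, p2 = 30%: (4.5 + 4.5)/30 = 30%, no distance from the Acquired Resistance value.
- At 15:15, p2 = 50%: (4.5 + 7.5)/30 = 40%, 10 points above it.
- At 15:15, p2 = 70%: (4.5 + 10.5)/30 = 50%, 20 points above it.
- Mix alone, p2 = 50%: 15:10 gives (4.5 + 5)/25 = 38%; 10:15 gives (3 + 7.5)/25 = 42%.

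The movement caused by the mix is thus only about 2 points either side of 40%. The larger effect is that the pooled value is an average of two populations.

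**5. Precision.** Exact (Clopper-Pearson) 90% intervals, assuming no censoring before one year:

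- 3/10: 8.7% to 60.7%
- 4/15: 9.7% to 51.1%
- 5/15: 14.2% to 57.7%
- 9/30 pooled: 16.6% to 46.5%
- 3/15: 5.7% to 44.0%, and 9/15: 36.0% to 80.9%, which overlap

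**The case against.** The best defence is that pooling 30 patients for precision is a reasonable choice in a small trial, and that the plan does not forbid cohort-level display. The opening statement of 8.1 covers the secondary outcomes too, and the Kaplan-Meier curves carry no enrolment condition, so one-year OS could be read from curves drawn by cohort at any size. The cohorts also overlap: both definitions accept at least 5 months of stable disease on earlier treatment. Finally, cohort-level intervals are so wide that even 3/15 and 9/15 overlap.

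Most of this stands, and it rules out three stronger readings that a reader might infer:

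- *That one-year OS will be available only pooled and only at 30 patients.* The text does not say so. The premise about full enrolment sits in one sentence and may be a planning assumption.
- *That the analysis below 30 is wholly open.* The parallel-cohort statement can serve as the default. The absence of an explicit rule is a secondary wording point, even though 30 may well not be reached.
- *That pooling hides a real survival difference.* The documents do not show how far the cohorts differ; the 30% to 70% range is an assumption.

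The defence does not answer the stated rule itself. Where 8.1 is explicit about one-year OS, it combines the cohorts, and the result does not match the hypothesis in 3.2. Wide intervals argue for calling cohort figures descriptive, not for omitting them.

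**Conclusion.** The point holds as a low-severity improvement. The pooling rule in 8.1 produces a one-year OS that mixes patients entering with progression and patients entering with stable disease, depends on the cohort mix, and does not address the first limb of the 3.2 hypothesis. Even the Acquired Resistance cohort is not an exact match for that limb, since intervening therapies are allowed, but it is the nearer population.

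The size is not known from the documents. Under the assumed range it is 0 to 20 points between the pooled and the Acquired Resistance value at 15:15, and zero if the cohorts are alike. The endpoint is secondary and descriptive: no test, decision rule or error rate is affected, and the response-rate design reproduces as stated.

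**What to change.** In 8.1, state that:

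- Kaplan-Meier one-year OS and one-year PFS will be reported with 90% confidence intervals separately for each cohort, at whatever size it reaches;
- the disease control rate with its 90% confidence interval will be reported by cohort, noting that stable disease is an entry condition in the Suboptimal Benefit cohort;
- pooled one-year OS is kept as a supplementary descriptive figure at whatever total is reached, with the cohort sizes given beside it.

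This also settles what applies below 30 patients. It costs a few sentences and needs no extra patients, visits or data. The downside is imprecision: at 30% OS the normal-approximation half-width, 1.645 × √(0.3 × 0.7/n), is about 24 points at n = 10 and 19 at n = 15, against 14 at n = 30. The cohort figures should be labelled descriptive and not used to compare the cohorts formally.

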#### **5.9 Subject Withdrawal/Discontinuation Criteria**

Subjects may withdraw consent at any time for any reason or be dropped from the trial at the discretion of the investigator should any untoward effect occur. In addition, a subject may be withdrawn by the investigator or the Sponsor if enrollment into the trial is inappropriate, the trial plan is violated, or for administrative and/or other safety reasons. Specific details regarding discontinuation or withdrawal are provided in Section 7.1.4 – Other Procedures.

A subject must be discontinued from the trial for any of the following reasons:

- The subject or legal representative (such as a parent or legal guardian) withdraws consent.
- Confirmed radiographic disease progression (=2nd scan within 4-8 weeks)

*Note:* For unconfirmed radiographic disease progression, please see Section 5.7.3

*Note:* A subject may be granted an exception to continue on treatment with confirmed radiographic progression if clinically stable or clinically improved, please see Section 5.7.3

- Unacceptable adverse experiences as described in Section 5.2.1.2
- Intercurrent illness that prevents further administration of treatment
- Investigator's decision to withdraw the subject
- The subject has a confirmed positive serum pregnancy test
- Noncompliance with trial treatment or procedure requirements
- The subject is lost to follow-up
- Completed 12 months of uninterrupted treatment with pembrolizumab or 18 administrations of study medication, whichever is later.

- Administrative reasons

The End of Treatment and Follow-up visit procedures are listed in Section 6 (Protocol Flow Chart) and Section 7.1.5 (Visit Requirements). After the end of treatment, each subject will be followed for 30 days for adverse event monitoring (serious adverse events will be collected for 90 days after the end of treatment as described in Section 7.2.3.1). Subjects who discontinue for reasons other than progressive disease will have post-treatment follow-up for disease status until disease progression, initiating a non-study cancer treatment, withdrawing consent or becoming lost to follow-up. After documented disease progression each subject will be followed by telephone for overall survival until death, withdrawal of consent, the end of the study, or 2 years beyond the last administration of study drug, whichever occurs first.

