#### **7.1.1.5.3 Subsequent Anti-Cancer Therapy Status**

The investigator or qualified designee will review all new anti-neoplastic therapy initiated after the last dose of trial treatment. If a subject initiates a new anti-cancer therapy within 30 days after the last dose of trial treatment, the 30 day Safety Follow-up visit must occur before the first dose of the new therapy. Once new anti-cancer therapy has been initiated the subject will move into survival follow-up.

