### **7.2.8.5 Follow-up Visits**

Subjects who discontinue trial treatment for a reason other than disease progression will move into the Follow-Up Phase and should be assessed every 8-12 weeks ( $\pm$  7 days) by radiologic imaging to monitor disease status. After 1 year, the imaging time point will occur every 12-16 weeks ( $\pm$  7 days). Every effort should be made to collect information regarding disease status until the start of new anti-neoplastic therapy, disease progression, death, end of the study or if the subject begins retreatment with pembrolizumab as detailed in Section 7.1.5.5. Information regarding post-study anti-neoplastic treatment will be collected if new treatment is initiated.

Protocol #: UC IRB17-1539

Version Date: 1/23/2018

Subjects who are eligible to receive retreatment with pembrolizumab according to the criteria in Section 7.1.5.5 will move from the follow-up phase to the Second Course Phase when they experience disease progression.

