#### **7.2.8.5.1 Survival Follow-up**

Once a subject experiences confirmed disease progression or starts a new anti-cancer therapy, the subject moves into the survival follow-up phase and should be contacted by telephone approximately every 12 to 16 weeks to assess for survival status until death, withdrawal of consent, or the end of the study, whichever occurs first OR at most 2 years out from the last patient receiving pembrolizumab.

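### PFS and duration of response have no rule for new anticancer therapy, yet disease assessment stops when it starts, so a switcher who later dies is counted progression-free until death

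*Combined protocol and SAP*

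**What the plan says.** **Endpoint definitions (Section 8.1, Secondary Outcome).** For PFS, "the latter endpoint will be defined as the time from enrollment until disease progression or death from any cause". For the other endpoint, "Duration of response will be determined as the time from response until disease progression or death among the subset of patients who respond". The section specifies Kaplan-Meier estimation and 90% intervals for the medians of PFS and overall survival (OS). It contains no censoring rule and does not mention new anticancer therapy, and no other section supplies either.

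**Follow-up.** Under Section 5.9, patients who stop for reasons other than progression have "follow-up for disease status until disease progression, initiating a non-study cancer treatment, withdrawing consent or becoming lost to follow-up". Section 7.2.8.5 has the same end point: "Every effort should be made to collect information regarding disease status until the start of new anti-neoplastic therapy, disease progression, death". Section 7.1.1.5.3 adds: "Once new anti-cancer therapy has been initiated the subject will move into survival follow-up". In that phase, per Section 7.2.8.5.1, the patient "should be contacted by telephone approximately every 12 to 16 weeks to assess for survival status until death".

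**Role of the endpoints.** 1-year PFS is a secondary objective (Section 3.2). Duration of response is analysed in Section 8.1 but is not listed as an objective.

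**The concern.** The two sets of rules do not fit together. The endpoint runs to progression or death. After a switch, progression is no longer looked for, but death is still recorded. For a patient who switches before documented progression, PFS then becomes survival time, partly under another drug's effect.

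The protocol foresees such patients. Section 7.2.8.5.1 treats confirmed progression and new therapy as alternative triggers for survival follow-up. Patients may also stop without progression for toxicity, intercurrent illness, investigator decision or completed treatment (Section 5.9), or after a complete response (Section 5.9.1).

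At stake are 1-year PFS, median PFS and duration of response in a single-arm trial of at most 30 patients, with no comparator to share the distortion. One patient is 1/30 = 3.3 percentage points if the cohorts are pooled. Duration of response may rest on about 0.20 × 15 = 3 responders per cohort at the target rate. Patients with documented progression before switching are not affected.

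**Working it through.** **1. The rules applied to two invented records.**

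- *PFS.* Stable disease, stops at month 2, other therapy at month 3, unseen progression at month 5, death at month 14. True PFS is 5 months and at most 3 were observed. Section 8.1 as written gives an event at 14 months.
- *Duration of response.* Response at month 2, other therapy at month 4 without progression, death at month 15. As written: 15 − 2 = 13 months, of which at most 4 − 2 = 2 were observed.

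**2. Direction.** Death cannot precede progression in a patient who progresses. Replacing a missed progression date by the death date therefore lengthens the recorded time or leaves it unchanged.

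**3. Size.** The plan states no PFS or duration-of-response figure, so there is nothing to reproduce. The only document input is that about 30% are alive at one year (Section 4.2.4.1). The rest is assumed:

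- Progression is exponential with median 3 months: λ = ln 2 / 3 = 0.2310 per month.
- A share s switches before progression, independently of prognosis: switching hazard μ = λs/(1 − s).
- Survival after progression is exponential with hazard γ, set so that 1-year OS is 30%.

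Write J(a) = (e^(12a) − 1)/a. Then:

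- True PFS(12) = e^(−12λ) = 0.5^4 = 0.0625.
- OS(12) = e^(−12λ) + λe^(−12γ) J(γ − λ). With γ = 0.1810 this is 0.0625 + 0.02633 × 9.02 = 0.300.
- PFS(12) as written = e^(−12λ) + λe^(−12γ) [J(γ − λ) − J(γ − λ − μ)].

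For s = 20%: μ = 0.0578, and the excess is 0.02633 × (9.02 − 6.73) = 0.060.

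| Switch before progression | μ | Excess | 1-year PFS as written | Median PFS as written | Excess patients in 30 |
|---|---|---|---|---|---|
| 4.2% | 0.0101 | 0.0125 | 7.5% | 3.05 months | 0.4 |
| 10% | 0.0257 | 0.0300 | 9.2% | 3.13 months | 0.9 |
| 20% | 0.0578 | 0.0603 | 12.3% | 3.30 months | 1.8 |
| 30% | 0.0990 | 0.0904 | 15.3% | 3.56 months | 2.7 |

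The truth in every row is 6.2% and 3.0 months.

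**4. Other inputs.** Refitting γ to 30% alive at one year, with s = 20%: a true median of 2 months takes 1-year PFS from 1.6% to 8.8%; a true median of 4 months takes it from 12.5% to 16.8%.

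Section 4.2.4.1 also gives a median OS of at most 6 months, and the model above has 8.2. Setting γ = ln 2 / 2 = 0.3466 makes median OS exactly 6 months, with 15.6% alive at one year. The four rows then become 6.9%, 7.8%, 9.4% and 10.8%.

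**5. Censoring at the switch.** With independent switching it returns 6.2% and 3.0 months, but only because independence was assumed. In an informative example, 20% of patients switch at 80% of their time to progression and survive a mean of 1 to 2 months after progression. Censoring then gives about 9.5% at one year and a median of 3.7 months. The rule as written gives about 6.6% to 7.3% and 3.2 to 3.4 months. Counting the switch as an event gives about 5.6% and 2.9 months.

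**The case against.** **Silence is not a rule for living switchers.** A reader might infer that a switcher still alive stays progression-free to the last telephone call. Section 8.1 gives no censoring date, so a statistician could equally censor at the last scan. This stands: only deaths after a switch follow from the text. For living switchers the same inflation occurs only if they are censored at last contact.

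**Switching before progression may be uncommon.** A reader might take such records as typical, and the documents do not support that. Section 7.4 counts clinical as well as radiographic progression, so a switch for clinical deterioration would usually follow a recorded event. Section 8.1 describes a setting without alternative treatments. Section 4.3.1.2 reports 4.2% stopping pembrolizumab alone for related adverse events. That is not a switching rate, but at that level the 1-year shift is only about 1.3 points. The 10% to 30% range is assumed.

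**The effect is small against the trial's precision.** With 30 patients and a 3-month median, the 11th and 20th ordered times give a 90% interval for the median of about 1.9 to 4.5 months. The median moves by at most about 0.6 months in the 3-month table. This stands for the median; 1-year PFS moves more in relative terms.

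**Censoring is not a cure.** It is tempting to say that it restores the true values. Step 5 shows that it can be more optimistic than the present text when patients switch because they are about to progress. This stands and shapes the fix.

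What the objection does not remove is the clash itself: the definition needs progression data that the follow-up plan stops collecting. Expecting sensible censoring at analysis leaves the choice until after the data of an open-label trial are known.

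**Conclusion.** The point holds in limited form. Under Section 8.1 as written, a patient who starts other anticancer therapy before documented progression and later dies has PFS, and duration of response if a responder, dated at death. For switchers still alive the censoring date is missing. Relative to fully observed progression, the effect on both endpoints is upward or nil.

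With a true median PFS of 3 months, independent switching and 30% alive at one year, 1-year PFS rises from 6.2% to between about 7.5% (4.2% switching) and 15% (30%). With the shorter survival also given in Section 4.2.4.1, the range is about 7% to 11%. The switching share, the distributions and the independence are assumptions, so the documents cannot say how large the bias will be in this trial.

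The response-rate rule and OS are unaffected. This should be corrected, but it does not threaten the primary conclusion.

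**What to change.** In Section 8.1, add to both definitions:

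- Patients who start non-study anticancer therapy without prior documented progression, clinical or radiographic, are censored at the last tumour assessment on or before that start.
- Patients alive without progression are censored at their last tumour assessment, not at telephone contact.
- A sensitivity analysis counts the start of new therapy as an event, because switching may be informative. Report it beside the main estimate.

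Leave OS unchanged, with all patients followed for death as planned.

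The cost is SAP wording and one extra analysis. New-therapy information is already to be collected (Sections 7.1.1.5.3 and 7.2.8.5), so no visits, scans or patients are added. There will be slightly fewer observed PFS and duration-of-response events, and the estimates will usually, but not always, be less favourable. Continued scanning after a switch would also close the gap, but would need new assessments.
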